Appendix C ESA and Parenteral Iron Dose-Adjustments

Weeks 1 - 4

- ESA doses are not to be adjusted or held during Weeks 1 through 4 unless one or more confirmed hemoglobin values (i.e., at least 2 consecutive measurements) or the patient's clinical status necessitates such due to a clear and present safety risk
- Parenteral iron doses are not to be adjusted or held during Weeks 1 through 4
- Patients not receiving parenteral iron products during Screening must not be started on these during Weeks 1 through 4
- The Medical Monitor must be contacted prior to any contemplated ESA or parenteral iron dose changes

Weeks 5 – 24

- Changes to ESA dosing must be based on hemoglobin values that have been confirmed (i.e., at least 2 consecutive measurements)
- Do not increase the dose more frequently than once every 4 weeks. The recommended dose increase at any given time is 25%
- Decreases in dose may occur more frequently than once every 4 weeks. The recommended minimum duration between dose reductions is 3 weeks
- If the hemoglobin rises rapidly (e.g., more than 1 g/dL in any 2-week period), reduce the dose by 25%. A greater reduction may be made, if rise in hemoglobin is unacceptably rapid
- The Medical Monitor must be contacted prior to any contemplated ESA dose changes that depart from the above protocol requirements and recommendations unless clinical urgency precludes this. If the Medical Monitor is not contacted in advance, please send a notification within 24 hours that an off-protocol ESA dose change was made
- Patients not receiving parenteral iron products must not be started on these during Weeks 5 through 24
- Parenteral iron doses are not to be adjusted or held during Weeks 5 through 24, unless approved by the Medical Monitor

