6. ERYTHROPOIESIS-STIMULATING AGENTS AND PARENTERAL IRON DOSES

ESA dosing will be summarized separately for EPOGEN (epoetin alfa), ARANESP (darbepoetin alfa) and MIRCERA (methoxy polyethylene glycol-epoetin beta) respectively. Historic ESA doses prior to randomization will be summarized weekly by treatment group for the pharmacodynamic analysis population. The mean weekly dose from Week -10 through Week -1 will also be computed for all ESAs. Percent change from baseline in ESA dose, change in ESA dose with ESA normalized to EPOGEN units, and change in ESA to a threshold value will also be computed with all ESAs pooled.

The following analyses will be performed:

- Comparison of the mean weekly ESA dose expressed in EPOGEN units prior to randomization to the post-randomization mean weekly dose for each 4-week interval in the Treatment and Safety Follow-up periods (e.g. Weeks 1-4, 5-8, etc). Inferential statistics will be performed for the Week 8-12 and the Week 1-4 periods.
 - Conversion of MIRCERA and ARANESP doses to EPOGEN units will be as follows:

$$\text{MIRCERA or ARANESP dose in mcg} * 300 = \text{EPOGEN unit equivalent dose}$$

- The percentage change from baseline with all 3 ESAs combined will be calculated for each 4-week interval in the Treatment and Safety Follow-up periods (e.g. Weeks 1-4, 5-8, etc). Inferential statistics will be performed for the Week 8-12 and the Week 1-4 periods.
- The number and percentage of subjects with dose change by +/- $\geq 25\%$, +/- $\geq 50\%$, and +/- $\geq 100\%$ will be computed for each 4-week interval in the Treatment and Safety Follow-up periods (e.g. Weeks 1-4, 5-8, etc).

Calculation of the Baseline ESA Dose

The baseline dose will be the baseline mean weekly dose for each ESA as defined below multiplied by 4.

- For EPOGEN, the baseline will be the mean weekly dose based on the 2 weeks immediately prior to randomization multiplied by 4.

- For ARANESP and MIRCERA, the baseline will be the mean weekly dose based on the 2 doses immediately prior to randomization multiplied by 4.
- The baseline dose will be normalized as the average dose per week during the time period of the doses used to define the baseline multiplied by 4.

Calculation of the Post-Baseline ESA Dose

- The post-baseline dose will be calculated based on the sum of all doses during a given time interval and will be expressed as the average dose per week during that time period multiplied by 4 or the number of weeks in the interval.

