7.2 SECONDARY PHARMACODYNAMIC ANALYSES

Endpoints:

1. Change from baseline (mean of Full Screening and Day 1 values) in hsCRP to the mean of Weeks 10-12
2. Change from baseline (mean of Full Screening and Day 1 values) in SAA to Week 4 between treatment groups
3. Change from baseline (mean of Full Screening and Day 1 values) in SAA to the mean of Weeks 10-12
4. Change from baseline (mean of Full Screening and Day 1 values) in the free IL-6 to Week 4 between treatment groups
5. Change from baseline (mean of Full Screening and Day 1 values) in Hemoglobin to Week 4
6. Change from baseline (mean of Full Screening and Day 1 values) in Hemoglobin to Week 10-12
7. Change from baseline (mean of Full Screening and Day 1 values) in Hemoglobin to Week 10-12, excluding hemoglobin values following a change in the total weekly ESA dose. A change is defined as the first time when the ESA weekly dose goes up by >25% or down by >25% relative to the previous week's dose.
8. Change from baseline (weekly mean of Full Screening) in ERI to the mean of Weeks 9-12 and Weeks 10-12

- a. The Screening ERI is defined as the ERI used to qualify the patient for the study per Inclusion Criterion #14
9. Change from baseline (mean of Screening and Day 1 values) in TSAT to Week 4
10. Change from baseline (mean of Full Screening and Day 1 values) in TSAT to Weeks 10-12
11. Change from baseline (mean of Screening and Day 1 values) in the CHr to Week 4
12. Change from baseline (mean of Full Screening and Day 1 values) in the CHr to Weeks 10-12
13. Change from baseline (mean of Full Screening and Day 1 values) in serum pre-albumin to the mean of Weeks 10-12
14. Change from baseline (mean of Full Screening and Day 1 values) in serum albumin to Week 12

Analysis Set:

Pharmacodynamic analysis population

Method:

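### SAP endpoint 7 excludes hemoglobin only after an ESA move of more than 25% from the previous week, so it cannot catch the protocol's own 25% steps, and it leaves weekly dose undefined

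*SAP*

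**What the plan says.** SAP 7.2, endpoint 7, takes the change in hemoglobin from baseline to Weeks 10–12, "excluding hemoglobin values following a change in the total weekly ESA dose". The trigger is: "A change is defined as the first time when the ESA weekly dose goes up by >25% or down by >25" percent, "relative to the previous week's dose". The same definition stands in SAP 1.2.3.2 and, for the interim analysis, in SAP 10.2. Endpoint 7 is analysed by ANCOVA with confidence intervals and p-values.

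For Weeks 5–24, Protocol Appendix C says: "The recommended dose increase at any given time is 25" percent. For a rapid hemoglobin rise it says: "reduce the dose by 25%. A greater reduction may be made". On spacing it says "Do not increase the dose more frequently than once every 4 weeks" and "The recommended minimum duration between dose reductions is 3 weeks". SAP 2.5.1 restates all of this.

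SAP 6 reports ESA changes with inclusive cut-offs: "The number and percentage of subjects with dose change by" at least 25%, 50% or 100% in either direction, by 4-week interval.

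Endpoint 7 does not say whether weekly dose is prescribed or administered, how missed or held doses count, or how an ESA given less often than weekly is converted.

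**The concern.** The endpoint is meant to show hemoglobin undisturbed by ESA adjustment. Its threshold sits just above the step size that the protocol recommends, so hemoglobin that follows a protocol-conforming step stays in. Comparing each week only with the week before means that a series of such steps is never recognised, however far the dose has drifted from baseline.

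Protocol 3.5.3 expects hemoglobin to rise, ESA requirements to fall, or both, on active drug. If that happens, retained 25% reductions on COR-001 and retained 25% increases on placebo would both tend to shrink the hemoglobin difference that endpoint 7 is meant to isolate.

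The undefined weekly dose brings a second risk. On some readings the rule drops values from patients whose regimen never changed. Two placebo patients in each of up to six cohorts gives about 12 in the pooled control group, so spurious losses there would matter. The same rule feeds the interim analysis that guides program planning.

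**Working it through.** The plan states no figure for this rule, so there is none to reproduce. I applied the rule as written: c = D(w)/D(w−1) − 1, where D is the weekly ESA dose. Values after the first week with |c| > 0.25 are dropped.

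**Inputs.** The threshold and reference come from SAP 7.2. Step sizes and spacing come from Appendix C. Thrice-weekly epoetin is an assumption: Protocol 3.6 gives three dialysis contacts a week, not an ESA frequency.

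**1. One conforming step, starting with the week.**
- Increase: 1.25/1 − 1 = +0.25. Not above 0.25, so not caught.
- Reduction: 0.75/1 − 1 = −0.25. Not caught.

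**2. Successive conforming steps.** Each has |c| = 0.25, so none is caught. Relative to the starting dose:
- Increases at Weeks 5 and 9 (4 weeks apart): 1.25² − 1 = +56.3%.
- Reductions at Weeks 5 and 8 (3 weeks apart): 0.75² − 1 = −43.8%.
- A third reduction at Week 11: 0.75³ − 1 = −57.8%.

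Reversals are treated unevenly. Undoing a 25% reduction is 1/0.75 − 1 = +33.3% and is caught. Undoing a 25% increase is 1/1.25 − 1 = −20% and is not.

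**3. The undefined weekly dose.** If D is the dose administered in the calendar week:

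| Situation, no regimen change | c | Excluded afterwards? |
|---|---|---|
| One of three weekly doses missed | 2/3 − 1 = −33.3% | Yes |
| One of two weekly doses missed | 1/2 − 1 = −50% | Yes |
| Once-weekly dose missed | −100% | Yes |
| Every-two-week ESA, off-week, not divided by interval | −100% | Yes |

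If D is the prescribed dose divided by its interval, none of these is caught.

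As an illustration only, assume three doses a week and independent misses with probability q per dose. A miss in Weeks 1–9 (27 doses) removes all Week 10–12 values. The chance of at least one is 1 − (1 − q)^27, which is 24%, 42% and 75% for q = 1%, 2% and 5%. The documents give no miss rate.

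**4. Would changing > to ≥ be enough?** It catches a 25% step that starts with the week. On administered dose with three sessions, it does not catch one that starts mid-week:
- From session 2: (1 + 2 × 1.25)/3 − 1 = +16.7%, then 3.75/3.5 − 1 = +7.1%.
- From session 3: (2 + 1.25)/3 − 1 = +8.3%, then 3.75/3.25 − 1 = +15.4%.

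Missed doses still trigger. Compared with baseline, the first full week after either step is 3.75/3 − 1 = +25%, which an inclusive cut-off catches. The reference and the dose definition therefore need changing as well as the sign.

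**The case against.** The strongest reply is that the rule is not broken, only loosely worded.

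- **Real changes are caught.** A reader might infer that the rule fires on missed doses in place of true changes. The text does not support that. Any move above 25% trips it, including the larger reduction that Appendix C permits. This stands.
- **25% is a recommendation.** Appendix C gives 25% as the recommended increase, and as the reduction only for a rapid rise; it sets no size for other reductions. Actual or rounded steps may differ. This stands, and it limits the size of the problem.
- **Missed doses depend on the reading.** The Amendment 2 rationale for Inclusion 8 separates missed doses from a change in total weekly dose, which favours prescribed dose. SAP 6, which sums all doses in an interval, favours administered dose. Endpoint 7 settles neither, so the −33.3% trigger is conditional.
- **Long-interval ESAs.** A reader might infer that every patient on such an ESA is lost from Weeks 10–12. That takes the least sensible reading. Inclusion 14 divides the dose by its interval, and the SAP is to be read with the protocol. What remains is a missing cross-reference.
- **SAP 6 measures something else.** It counts interval changes, not a weekly trigger, so the boundaries need not match. Even so, a patient at exactly 25% could count as changed there and unchanged here.
- **Limited reach.** This is one of 14 secondary endpoints in SAP 7.2. Endpoint 6 is the unrestricted version, ERI and ESA dose are analysed directly, and the interim has no stopping rules. This stands.

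The sensitivity analyses in SAP 7.5 do not repair the gap. They address off-protocol ESA or iron dosing and data after a first SAE. A conforming 25% step after Week 4 is neither.

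**Conclusion.** The rule is wrong as written, in a limited way. That a strict 25% threshold misses a 25% step, and that successive steps can reach +56.3% or −43.8% unseen, follows from the text alone and needs no assumption beyond steps of exactly the stated size. The endpoint therefore keeps some of the ESA effects it was written to remove.

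The second part is an ambiguity, not a demonstrated malfunction. Exclusion without a regimen change happens only if weekly dose means administered dose, and the −33.3% figure also assumes thrice-weekly epoetin.

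Endpoint 7 should not be described as hemoglobin free of ESA: patients stay on ESA throughout, and the aim is hemoglobin before a dose change. The number of patients affected and the shift in the estimate cannot be derived from the documents. The primary pharmacodynamic endpoints are unaffected.

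**What to change.** In SAP 1.2.3.2, 7.2 and 10.2, define a change as 25% or more, up or down, in the prescribed weekly-equivalent dose (dose divided by dosing interval, as in Inclusion 14) relative to the baseline prescribed dose. State that missed or held doses without a prescription change do not count. Keep endpoint 6 as the main hemoglobin analysis and label endpoint 7 supportive.

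This alters the analysis only; ESA management is untouched. The work is one definition in three places and one derivation. The price is that more Week 10–12 values will be excluded after protocol ESA steps. The exclusion is selective, because the stated reduction follows a rapid hemoglobin rise and so removes values from patients who responded. A single step below 25% still escapes until later steps carry the dose to the cut-off.

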
Pharmacokinetic and PK-PD Modeling:
	
 • Serum COR-001 concentrations will be subjected to PK modeling and secondary PK parameters such as maximum serum drug concentrations (C_{max}), area under the serum drug concentration-time curve (AUC) and terminal elimination half-life ($t_{1/2}$) will be calculated. • The free (unbound to COR-001) and total (free + bound) IL-6 AUC will be described • The change in plasma concentration of COR-001 from pre-dialysis to post-dialysis will be described • The relationship between COR-001 pharmacokinetics and primary pharmacodynamic endpoints, specifically free and total serum IL-6, high-sensitivity C-reactive protein (hsCRP) and serum amyloid A (SAA) will be described.

Safety Endpoints:
	
Primary
 
 1. Characterization of the MTD or to establish that the highest dose examined did not exceed the MTD 
Secondary
 
 1. Description of the frequency of DLTs (defined in Section 4.4) by treatment group and dose 2. Description of the frequency of the events of interest by treatment group and dose (defined in Section 9.3) 3. Description of additional safety assessments by treatment group and dose: adverse events, vital signs, ECG, clinical laboratory, and anti-drug antibodies (binding and neutralizing)

Primary Pharmacodynamic Endpoints
	
 • Change from baseline (mean of Screening and Day 1) in the SAA and hsCRP to Week 4 between treatment groups

Secondary Pharmacodynamic Endpoints
	
Mean differences between placebo and COR-001-treated patients will be determined for the following parameters:
 
 • Change from baseline (mean of Screening and Day 1 values) in TSAT to Week • Change from baseline (mean of Screening and Day 1 values) in the CHR to Week 4 • Change from baseline (mean of Screening and Day 1 values) in hsCRP to the mean of Weeks 10-12. • Change from baseline (mean of Screening Period and Day 1 values) in SAA to the to the mean of Weeks 10-12 • Change from baseline (mean of Screening Period and Day 1 values) in serum pre-albumin to the mean of Weeks 10-12 and albumin to Week 12 • Change from baseline (weekly mean of Screening) in ERI to Week 4 • Change from baseline (weekly mean of Screening) in ERI to the mean of Weeks 8 - 12 
Exploratory pharmacodynamics endpoints are described in Section 11.4.4

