Following the 12-week Treatment Period, patients will be followed for an additional 12 weeks for safety in the Safety Follow-Up Period. The patient's will have completed their primary study participation at Week 24 (end of the Safety Follow-Up Period). Sparse blood samples will be additionally collected on Week 35 for anti-drug antibodies, pharmacokinetics, and IL-6 measurements as part of an Extended Follow-Up Period.

3.1.1 *Pharmacokinetic and PK-PD Modeling*

- Serum COR-001 concentrations will be subjected to PK modeling and secondary PK parameters such as maximum serum drug concentrations (C_{max}), area under the serum drug concentration-time curve (AUC) and terminal elimination half-life ($t_{1/2}$) will be calculated.
- The free (unbound to COR-001) and total (free + bound) IL-6 AUC will be described
- The change in serum concentration of COR-001 from pre-dialysis to post-dialysis will be described
- The relationship between COR-001 pharmacokinetics and primary pharmacodynamic endpoints, specifically free and total serum IL-6, high-sensitivity C-reactive protein (hsCRP) and serum amyloid A (SAA) will be described.

3.1.2 *Safety Endpoints*

Primary

- Characterization of the MTD or to establish that the highest dose examined did not exceed the MTD

Secondary

- Description of the frequency of DLTs (defined in [Section 4.4](#)) by treatment group and dose
- Description of the frequency of the events of interest by treatment group and dose (defined in [Section 9.3](#))
- Description of additional safety assessments by treatment group and dose: adverse events, vital signs, ECG, clinical laboratory, and anti-drug antibodies (binding and neutralizing)

3.1.3 *Pharmacodynamic Endpoints*

Data from COR-001-treated patients from Cohorts not exceeding the MTD will be pooled and data from all placebo patients will be pooled for the pharmacodynamic endpoint analyses.

Primary

- Change from baseline (mean of Screening and Day 1) in the SAA and hsCRP to Week 4 between treatment groups

Secondary

- Mean differences between placebo and COR-001-treated patients will be determined for the following parameters:
- Change from baseline (mean of Screening and Day 1 values) in TSAT to Week 4
- Change from baseline (mean of Screening and Day 1 values) in the CHr to Week 4
- Change from baseline (mean of Screening and Day 1 values) in hsCRP to the mean of Weeks 10 – 12
- Change from baseline (mean of Screening and Day 1 values) in SAA to the mean of Weeks 10 – 12

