1.2.3.2 Secondary Pharmacodynamic Endpoints

- Change from baseline (mean of Screening and Day 1 values) in TSAT to Week 4
- Change from baseline (mean of Screening and Day 1 values) in the CHr to Week 4
- Change from baseline (mean of Full Screening and Day 1 values) in hsCRP to the mean of Weeks 10-12
- Change from baseline (mean of Full Screening and Day 1 values) in SAA to the mean of Weeks 10-12
- Change from baseline (mean of Full Screening and Day 1 values) in serum pre-albumin to the mean of Weeks 10-12 and albumin to Week 12
- Change from baseline (weekly mean of Screening) in ERI to Week 4
- Change from baseline (weekly mean of Screening) in ERI to the mean of Weeks 8 – 12
- Change from baseline (mean of Full Screening and Day 1 values) in Hemoglobin to Week 4
- Change from baseline (mean of Full Screening and Day 1 values) in Hemoglobin to Week 10-12
- Change from baseline (mean of Full Screening and Day 1 values) in Hemoglobin to Week 10-12, excluding hemoglobin values following a change in the total weekly ESA dose. A change is defined as the first time when the ESA weekly dose goes up by >25% or down by >25% relative to the previous week's dose.
- Change from baseline (weekly mean of Full Screening) in ERI to the mean of Weeks 10 – 12
- Change from baseline (mean of Full Screening and Day 1 values) in TSAT to Week 10-12
-
- Change from baseline (mean of Full Screening and Day 1 values) in the CHr to Week 10-12
-
- Change from baseline (mean of Full Screening and Day 1 values) in serum albumin to Week 12

Exploratory Pharmacodynamic Endpoints

- Description of the systemic iron availability (TSAT, absolute reticulocyte count,

hemoglobin, CHr) over time

- Description of markers of malnutrition-inflammation (pre-albumin and albumin) over time
- Description of systemic iron stores (serum ferritin, hepatic and splenic iron content by MRI, and supplemental iron dose requirements) over time
- Description of ERI change from baseline (weekly mean during the Screening Period) through Week 24
- Description of changes ESA and parenteral iron dose requirements from baseline (weekly mean during the Screening Period) to Evaluation Period (Weeks 8 – 12) and through Week 24
- Description of changes in LV mass index from Screening to Week 12
Description of changes in pre-dialysis, post-dialysis, and delta-serum Troponin and NT-proBNP (defined as the difference between the pre- and post-dialysis troponin) from baseline (mean of Screening) to Weeks 10 – 11

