Number of patients (n), mean, standard deviation (SD), median, quartiles (Q1 and Q3), minimum (min) and maximum (max) values for the observed value and change from baseline will be reported. The difference in changes (COR-001 - Placebo) will be presented. An ANCOVA model including dose as a factor and baseline value as a covariate will be used. The least square means for each dose, the least square mean differences from placebo along with the associated 95% CIs and p-values will be presented. In addition, for change from baseline in TSAT to week 4, a shift table analysis with the categories: <20%, 20%-30%, >30% - 50%, >50% will be presented. The weekly mean of ERI will be calculated and presented for all ESAs combined based on the formula in [Section 1.2.3.2](#).

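### The SAP's ANCOVA for ERI covers only Weeks 9–12 and 10–12, so neither ERI secondary endpoint named in the protocol (Week 4, mean of Weeks 8–12) has a model-based comparison with placebo

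*SAP*

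**What the plan says.** **Protocol.** The Synopsis and Section 3.1.3 open the secondary pharmacodynamic list with "Mean differences between placebo and COR-001-treated patients will be determined for the following parameters". Two ERI items follow: change to Week 4, and "Change from baseline (weekly mean of Screening) in ERI to the mean of Weeks 8 - 12". Section 11.4.4 names the same two time points.

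**SAP endpoint list.** Section 1.2.3.2 carries both: "Change from baseline (weekly mean of Screening) in ERI to Week 4" and "Change from baseline (weekly mean of Screening) in ERI to the mean of Weeks 8 – 12". It adds a third that the protocol does not have: "Change from baseline (weekly mean of Full Screening) in ERI to the mean of Weeks 10 – 12".

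**SAP analysis list.** Section 7.2 has one ERI item, number 8: the change "in ERI to the mean of Weeks 9-12 and Weeks 10-12". For the endpoints in that list, an ANCOVA with dose as factor and baseline as covariate is fitted, and "the least square mean differences from placebo along with the associated 95% CIs and p-values will be presented".

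**Other SAP sections.** Section 7.3 summarises ERI change through Weeks 4, 12 and 24 by treatment group, descriptively. Section 6 plans inferential statistics for Weeks 1–4 and 8–12 and labels Weeks 8–12 as the endpoint, but for ESA dose, not ERI. Sections 7.5 and 10.2 mention ERI without giving a window.

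**The concern.** The list of endpoints and the list of analyses do not match for ERI. A programmer who follows SAP 7.2 literally would fit the model to two late windows. Neither of these is a protocol endpoint, and one is not defined as an ERI endpoint anywhere. The same programmer would produce no adjusted difference from placebo for the two endpoints that the protocol names.

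ERI is one of the hematologic endpoints for which Protocol 3.5.3 states an expected direction (a fall). Week 4 is also the ERI time point with the least interference from ESA changes, because Protocol Appendix C restricts ESA adjustment in Weeks 1–4 and allows it under guidance from Week 5. At stake is whether the study report contains the ERI comparisons that the protocol promised, on the windows it promised.

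**Working it through.** No power or sample-size figure bears on this point, so the check is a comparison of text.

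**Step 1: where each ERI time point appears**

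| ERI change from baseline to | Protocol secondary | SAP 1.2.3.2 secondary | SAP 7.2 ANCOVA | SAP 7.3 descriptive |
|---|---|---|---|---|
| Week 4 | yes | yes | no | yes |
| mean of Weeks 8–12 | yes | yes | no | no |
| mean of Weeks 9–12 | no | no | yes | no |
| mean of Weeks 10–12 | no | yes | yes | no |

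Protocol ERI endpoints that reach the ANCOVA: 0 of 2. ERI windows in SAP 7.2 that are protocol endpoints: 0 of 2.

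**Step 2: are other endpoints treated the same way?** Counting pre-albumin and albumin separately, the protocol has six other secondary pharmacodynamic endpoints. Their items in SAP 7.2 are:

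- TSAT to Week 4: item 9
- CHr to Week 4: item 11
- hsCRP to Weeks 10–12: item 1
- SAA to Weeks 10–12: item 3
- pre-albumin to Weeks 10–12: item 13
- albumin to Week 12: item 14

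That is 6 of 6, against 0 of 2 for ERI. The gap is specific to ERI.

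**Step 3: how the windows differ.** Weeks 8–12 spans 5 weeks. Weeks 9–12 drops Week 8 (1 of 5). Weeks 10–12 drops Weeks 8 and 9 (2 of 5).

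**Step 4: is there a reason in the documents?**

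- *Data availability:* no. The Schedule of Events has the hematology panel on Days 50, 57, 64, 71 and 78, that is, at each of Weeks 8 to 12.
- *Protocol version:* no. The SAP is written to Amendment 2, but its own Section 1.2.3.2 carries both protocol endpoints, and the Amendment 3 summary records no change of ERI window.
- *Recorded change:* no. SAP 12 lists none.
- *Consistency with ESA dose:* it points the other way. SAP 6 treats Weeks 8–12 as the endpoint window for ESA dose, which is the numerator of ERI.

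**Step 5: the baseline in the same item.** For Week 4 and Weeks 8–12, SAP 1.2.3.2 uses a weekly mean over Screening. For Weeks 10–12, it uses a weekly mean over Full Screening, as does SAP 7.2 item 8. Sub-item 8a then defines the Screening ERI as the value that qualified the patient under Inclusion Criterion 14. These are three descriptions of one covariate.

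**The case against.** **The protocol never required a test.** This is true. Protocol 11.4.4 says these variables are summarised with descriptive statistics, and the secondary list promises mean differences only. A reader might infer that a protocol-specified hypothesis test was dropped; the documents do not support that. What is missing is the between-group difference, together with the ANCOVA that the SAP itself applies to every other protocol secondary endpoint.

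**Week 4 is not ignored.** This is also true. SAP 7.3 summarises it by treatment group, and SAP 2.1 says generally that 95% confidence intervals will be estimated for pharmacodynamic endpoints. But 7.3 specifies no difference, and 2.1 names no model or contrast. Neither helps with the Weeks 8–12 mean.

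**The components of ERI are compared.** Hemoglobin at Week 4 has the ANCOVA (SAP 7.2 item 5), and ESA dose has inference for Weeks 1–4 and 8–12 (SAP 6). This reduces the loss, most of all at Week 4, when ESA doses are largely fixed. It does not replace a ratio endpoint. In the late period the components do not even share a window: hemoglobin is modelled at Weeks 10–12, ESA dose at Weeks 8–12.

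**Weeks 9–12 has a source, or is a slip for 8–12.** It is one of the regular four-week ESA-dose intervals in SAP 6, so it would be wrong to say that it appears nowhere else. It is still in no ERI endpoint list. If it is a slip, it needs correcting, and Week 4 is still absent from 7.2.

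**Weeks 10–12 is a sensible window.** It is the late window for hsCRP, SAA, hemoglobin, TSAT, CHr and pre-albumin in SAP 7.2. That is a good reason to keep it alongside the protocol endpoints, not in place of them.

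**Conclusion.** The point stands as a mismatch between endpoint list and analysis list. Neither protocol ERI secondary endpoint has a model-based comparison with placebo. One of them (Week 4) keeps a descriptive summary by group; the other (mean of Weeks 8–12) has no ERI analysis at all. This rests only on reading SAP 7.2 as written and on taking it as the sole place where the secondary ANCOVA is applied. It should be corrected, but it concerns secondary endpoints in a Phase 1/2 trial and leaves the primary safety and primary pharmacodynamic analyses untouched.

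Three stronger readings are not supported:

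- *That ERI is the leading measure of the anemia hypothesis.* Protocol 3.5.3 lists it with TSAT, hemoglobin, reticulocyte count, CHr, and ESA and iron doses, and the sample-size section (11.1) covers hsCRP, TSAT and CHr but not ERI.
- *That the shorter window costs much precision.* With equal correlation r between weekly values, the standard error of a 3-week mean relative to a 5-week mean is sqrt{[(1+2r)/3] / [(1+4r)/5]}. This is 1.29 at r = 0, 1.05 at r = 0.5 and 1.01 at r = 0.9. The documents give no r. Weekly ERI values share a target dry weight and a largely stable ESA dose, so independence is implausible.
- *That three late tests compete for selection.* SAP 7.2 models two windows and commits to presenting both; Weeks 8–12 has no model. The documents do not say which late window governs, but nothing in them shows a choice made on results.

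**What to change.** Four wording changes to the SAP:

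1. In Section 7.2, add ERI change to Week 4 and ERI change to the mean of Weeks 8–12, both with the stated ANCOVA, and identify them as the protocol-defined ERI endpoints.
2. Keep Weeks 10–12 and label it supportive.
3. Correct Weeks 9–12 to Weeks 8–12. If Weeks 9–12 is intended, label it an added analysis, list it in Section 1.2.3.2 and record it in Section 12.
4. Use one definition of the ERI baseline in Section 1.2.3.2, Section 7.2 item 8 and sub-item 8a.

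The cost is a SAP revision and two more runs of a model that is already specified. No new data are needed: the hematology panel is scheduled at each of the weeks concerned, and ESA doses are already summarised for Weeks 1–4 and 8–12 under SAP 6. The revision should be made before unblinding.
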